8.3.5. Clinical Laboratory Assessments

See Section 1.3 (SoA) for the timing and frequency.

8.3.5.1. Central Laboratory Assessments

All laboratory assessments at the Day 270 and 365/ET Visits will be performed by the central laboratory.

The Investigator must review the laboratory report, document this review, and record any clinically relevant changes occurring during the study. The laboratory reports must be filed with the source documents and uploaded into the EDC. Clinically significant abnormal laboratory findings are those that are not associated with the underlying disease, unless judged by the Investigator to be more severe than expected for the Participant's condition.

All protocol-required laboratory assessments must be performed in accordance with the laboratory manual and the SoA.

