8.4.5.2. AESIs Related to Other Medical Problems

Several medical problems are frequently observed in patients with diabetic peripheral neuropathy that should be considered AESIs. These medical problems are listed below by type of medical problem.

Infections and Infestations; Skin and Subcutaneous Disorders

Because patients with diabetic peripheral neuropathy are at an increased risk to develop skin lesions (e.g., blisters, ulcers) and various lower limb infectious complications (e.g., cellulitis, osteomyelitis) that may be associated with systemic infections (e.g., bacteremia, sepsis, or septic shock), all of these types of medical problems that occur between the Day 180 (VMDN-003-02) and the Day 365/ET (VMDN-003-2b) Visits will be considered AESIs. In addition, any amputations involving the lower extremity, development of Charcot foot, or other similar complications will also be considered AESIs.

Peripheral Arterial Disease

An overlap of DPN and peripheral artery disease (PAD) apparently exists in type 2 diabetic patients. ⁴⁶ Because Participants with DPN may develop signs or symptoms of PAD between the Day 180 (VMDN-003-2) and the Day 365/ET (VMDN-003-2b) Visits, detailed evaluations of Participants considered to have PAD will be considered AESIs.

Version 1.0 43 Final: 11 Feb 2021

Diabetic Neuropathies

Because Participants in this study may develop other types of diabetic peripheral neuropathies while in the study, the following events will be considered to be AESIs in Participants with DPN: diabetic mononeuropathy, diabetic mononeuropathy multiplex, and diabetic polyradiculopathy. The occurrence of these other types of peripheral neuropathies in a Participant with DPN may indicate a more severe form of DPN.

Because Participants in this study may develop various manifestations of autonomic neuropathy (typically involves the gastrointestinal, genitourinary tract, cardiovascular systems) after randomization, the clinical manifestations of diabetic autonomic neuropathy will be considered to be AESIs.

Glycemic Control

Hypoglycemia, hyperglycemia, hyperlipidemia, hypercholesterolemia, and hypertriglyceridemia are to be listed as AESIs based on the Common Terminology Criteria for Adverse Events (CTCAE) grading if they are Grades 3 or 4.

Metabolic complications of DM (such as diabetic ketoacidosis [DKA], hyperglycemic hyperosmolar non-ketotic coma, lactic acidosis, metabolic acidosis [overlaps with DKA]) are to be listed as AESIs.

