8.4.9. Disease-Related Events and/or Disease-Related Outcomes Not Qualifying as TEAEs or TESAEs

Except for signs and symptoms of diabetic peripheral neuropathy (i.e., numbness, pain, tingling or burning sensation, cramps, and increased sensitivity to touch), all disease-related events or disease-related outcomes qualify as TEAEs or TESAEs.

Version 1.0 46 Final: 11 Feb 2021

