9.3.2. Secondary Endpoints

The secondary efficacy endpoints include the following:

- Change in the means of the Worst Pain scores from the full BPI-DPN from the 7 days prior to the Day 0 Visit (Study VMDN 003 2) to the 7 days prior to the Day 270 Visit and the 7 days prior to the Day 365 Visit for Engensis compared to Placebo
- Proportion of Responders (≥ 50% reduction in the ADPSs from the full BPI-DPN) from the 7 days prior to the Day 0 Visit (Study VMDN-003-2) to the 7 days prior to the Day 270 Visit and the 7 days prior to the Day 365 Visit for Engensis compared to Placebo

Secondary safety endpoints include:

- Incidence of TEAEs and TESAEs for Engensis compared to Placebo
- Incidence of clinically significant laboratory values for Engensis compared to Placebo

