10.2.1. Definition of AE

Note the definitions for AEs and SAEs presented below also apply to TEAEs and TESAEs in this protocol.

AE Definition

- An AE is any untoward medical occurrence associated with the use of an investigational product or study procedure in a clinical study Participant whether or not considered related to the study intervention.
- NOTE: An AE can therefore be any unfavorable and unintended sign (including an abnormal laboratory finding), symptom, or disease (new or exacerbated) temporally associated with the use of study intervention or procedure.

Events Meeting the AE Definition

- Any abnormal laboratory test results (hematology, or clinical chemistry) or other safety
 assessments (e.g., ECG, radiological scans, vital signs measurements), including those
 that worsen from baseline, considered clinically significant in the medical and
 scientific judgment of the investigator (i.e., not related to progression of underlying
 disease).
- Exacerbation of a chronic or intermittent pre-existing condition including either an increase in frequency and/or intensity of the condition.
- New conditions detected or diagnosed after study intervention administration even though it may have been present before the start of the study.
- Signs, symptoms, or the clinical sequelae of a suspected drug-drug interaction.
- Signs, symptoms, or the clinical sequelae of a suspected overdose of either study intervention or a concomitant medication. Overdose per se will not be reported as an AE/TESAE unless it is an intentional overdose taken with possible suicidal/selfharming intent. Such overdoses should be reported regardless of sequelae.

Events **NOT** Meeting the AE Definition

- Any clinically significant abnormal laboratory findings or other abnormal safety
 assessments that are associated with the underlying disease, unless judged by the
 Investigator to be more severe than expected for the Participant's condition.
- The disease/disorder being studied or expected progression, signs, or symptoms of the

Version 1.0 61 Final: 11 Feb 2021

disease/disorder being studied, unless more severe than expected for the Participant's condition.

- Medical or surgical procedure (e.g., endoscopy, appendectomy): the condition that leads to the procedure is the AE.
- Situations in which an untoward medical occurrence did not occur (social and/or convenience admission to a hospital).

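### The protocol's definition of a clinically significant laboratory value turns on presumed cause, so the secondary safety endpoint of that name can omit expected-looking diabetic abnormalities in both arms

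*Protocol*

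**What the plan says.** Protocol 8.3.5.1 asks the Investigator to review each central laboratory report and then supplies a definition: "Clinically significant abnormal laboratory findings are those that are not associated with the underlying disease". The same sentence closes with an exception for such findings: "unless judged by the Investigator to be more severe than expected for the Participant's condition". Protocol 9.3.2 lists as a secondary safety endpoint "Incidence of clinically significant laboratory values for Engensis compared to Placebo". Protocol Section 3 and SAP 7.0 list the same endpoint. None of these places gives a criterion of its own.

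Three other protocol sections bear on the term:

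- **10.2.1, events that are AEs.** Abnormal results count when the Investigator considers them clinically significant, which is glossed as "not related to progression of underlying" disease.
- **10.2.1, events that are not AEs.** A bullet opens "Any clinically significant abnormal laboratory findings or other abnormal safety" and continues "assessments that are associated with the underlying disease", with the same severity exception.
- **8.4.9.** Apart from signs and symptoms of DPN, "all disease-related events or disease-related outcomes qualify as TEAEs or TESAEs".

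Separately, 8.4.5.2 says that "Hypoglycemia, hyperglycemia, hyperlipidemia, hypercholesterolemia, and hypertriglyceridemia are to be listed as AESIs" when they reach CTCAE Grade 3 or 4, with no test of cause.

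SAP 12.6 introduces its subsections as the methods for the safety endpoints. SAP 12.6.3 plans summaries by treatment and visit, low/normal/high shift tables against baseline, and counts of participants beyond fixed limits. It labels those counts as being of special interest and does not call them clinically significant.

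**The concern.** An exclusion of the kind used to decide what is reported as an AE is serving as the definition of an endpoint. An endpoint that compares laboratory abnormalities by arm would normally rest on how large or important the abnormality is. Here an abnormality that the Investigator attributes to the underlying disease, and regards as no worse than expected, does not qualify.

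Every participant has diabetes, so glucose, HbA1c, BUN, creatinine and lipid abnormalities are easily attributed to it. The concurrent Placebo arm already carries the disease background, so removing these values case by case mainly discards events. Metabolic values are also of some interest for this product, because Protocol Section 2 connects HGF with the pathophysiology of insulin resistance.

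Two sites could classify the same value differently and each cite the protocol. The site's classification matters because the synopsis lists clinically significant laboratory values as an item assessed alongside TEAEs, not as part of them.

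**Working it through.** The documents state no rate of clinically significant laboratory values, and safety is summarised without formal testing. There is therefore no planned figure to reproduce. The check compares the texts and counts analytes.

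**Step 1: apply each section to the same value.** Let D mean attributed to the underlying disease and S mean judged more severe than expected.

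| Abnormal value | 8.3.5.1 | 10.2.1 | 8.4.9 |
|---|---|---|---|
| Not D | Can be clinically significant | AE if judged clinically significant | Not addressed |
| D and S | Clinically significant | Not excluded by the disease bullet | Event qualifies as a TEAE unless a DPN sign or symptom |
| D, not S | Not clinically significant | May be called clinically significant, but is excluded as an AE | Event qualifies as a TEAE unless a DPN sign or symptom |

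The sections part company in the third row. Under 8.3.5.1 a value that is D and not S cannot be clinically significant, so the exclusion bullet in 10.2.1 would describe an empty class. That bullet has content only if clinical significance is judged apart from cause. The other 10.2.1 bullet ties significance to cause again, and 8.4.9 points away from any exclusion beyond DPN symptoms.

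**Step 2: what is the underlying disease?** No section defines it.

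- For diabetes: Protocol 2.3.1 describes a vitreous hemorrhage as probably due to underlying disease, which hardly fits a peripheral neuropathy. Section 10.2.1 also treats the disease being studied in a separate bullet.
- For DPN: it is the condition under study, and the exception in 8.4.9 is limited to DPN.

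Both readings are open to a site.

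**Step 3: count what is captured regardless of cause.** Analytes in Protocol 8.3.5.1.1 to 8.3.5.1.5: hematology 5 + kidney 2 + liver 7 + chemistry 13 (including HbA1c) + lipids 4 = 31.

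SAP 12.6.3 sets fixed limits for 11: glucose, triglycerides, LDL, potassium, hemoglobin, WBC, platelets, creatinine, AST, ALT and total bilirubin. That leaves 31 − 11 = 20 without one.

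The analytes most readily attributed to diabetes number 8: glucose, HbA1c, BUN, creatinine and four lipids.

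- With a limit, 4: glucose (> 320 mg/dL), creatinine (≥ 2 mg/dL), triglycerides (≥ 500 mg/dL), LDL (≥ 189 mg/dL).
- Without a limit, 8 − 4 = 4: HbA1c, BUN, total cholesterol, HDL.

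**Step 4: what can drop out.** On the diabetes reading, disease-attributed values of the first four that stay within the limits, and disease-attributed values of the other four at any level, enter the named endpoint only if the Investigator finds them more severe than expected. No reference level is given for that judgement.

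**The case against.** The strongest reply is that the laboratory analysis visible in the SAP does not use the criticised definition. The summaries, shift tables and fixed-limit counts in SAP 12.6.3 ignore cause, and no table of Investigator-judged significance is planned there. Marked glucose, creatinine, triglyceride and LDL values will be reported by arm, and Grade 3 or 4 glycemic and lipid events are AESIs. This stands as a limit on the harm. It does not settle the endpoint, because the SAP never says that these counts are the clinically significant laboratory endpoint.

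Other replies also have weight. The severity exception readmits the worst disease-associated values. If underlying disease means DPN, the metabolic values are not clearly excluded. The product argument is modest: Section 2 says HGF is expressed for up to 30 days, the last injection was at Day 104, and the first scheduled laboratory visit here is Day 270, which is 270 − 104 = 166 days later. The CRF and laboratory manual, which may govern flagging, are not available.

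A reader might infer four stronger things that the documents do not support:

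- **That the endpoint cannot show a treatment effect on these analytes.** The severity exception and the open meaning of underlying disease prevent that conclusion. It may be less able to show one.
- **That the rule favours one arm.** Investigators are blinded, so nothing in the documents suggests that it works differently by arm.
- **That a treatment difference shrinks by some stated number of points.** Any such figure would only restate assumed incidences and attribution rates.
- **That any trivial abnormality unrelated to disease must count.** Section 8.3.5.1 asks for clinically relevant changes, and 10.2.1 requires medical and scientific judgement.

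**Conclusion.** The point holds in a limited form. A stated rule, not merely a missing detail, allows disease-attributed abnormalities to be left out of a named secondary safety endpoint, and other protocol sections do not fit that rule. The conclusion depends on sites reading underlying disease as diabetes, which the text permits but does not require.

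What is at risk is the sensitivity of the endpoint and consistency between sites. The exposure is mainly expected-looking glucose, creatinine, triglyceride and LDL values within the SAP limits, and HbA1c, BUN, total cholesterol and HDL, which have no limit. No numerical size can be given from the documents. Correction is worthwhile because it is specific and inexpensive, but the point does not call the overall laboratory safety reporting into question.

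**What to change.** 1. In Protocol 8.3.5.1, define clinical significance for the endpoint by the size and importance of the abnormality and its change from the pre-dose VMDN-003-2 value, without regard to presumed cause.
2. Record presumed cause (underlying disease, yes or no) in a separate field, and show the split as supporting information.
3. Confine any disease exclusion to AE reporting in 10.2.1. Reconcile 8.3.5.1, 8.4.9 and 10.2.1, and define underlying disease.
4. In SAP 12.6.3, state which by-arm count is this secondary endpoint and whether the special-interest limits form part of it. Make sure that HbA1c, BUN, total cholesterol and HDL are covered.

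The cost is a protocol wording change, a CRF field with guidance, and a short SAP edit. No visit, test or treatment changes. The downside is that more values will be flagged in both arms, so the reported incidences will rise.

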8.3.5.1.1. Hematology

- White blood cell count
- Neutrophil (including calculated absolute neutrophil count)
- Hemoglobin
- Hematocrit
- Platelet count

8.3.5.1.2. Kidney Function Tests

- Blood urea nitrogen (BUN)
- Creatinine

8.3.5.1.3. Liver Function Tests

• Aspartate aminotransferase (AST)

Version 1.0 40 Final: 11 Feb 2021

- Alanine aminotransferase (ALT)
- Alkaline phosphatase
- Gamma-glutamyl transpeptidase (GGT)
- Total bilirubin
- Total protein
- Albumin

8.3.5.1.4. Clinical Chemistry

- Electrolytes (sodium, potassium, chloride, bicarbonate, calcium, inorganic phosphate, magnesium)
- Glucose (random collection, i.e., not necessarily fasting)
- Amylase
- Lipase
- Lactate dehydrogenase
- Creatine kinase
- HbA1c

8.3.5.1.5. Lipid Profile

- Total cholesterol
- High-density lipoprotein cholesterol (HDL-C)
- Low-density lipoprotein cholesterol (LDL-C)
- Triglycerides

8.3.5.1.6. Additional Tests

- Urine pregnancy test
- Urine drug analysis

8.3.6. Retinal Fundoscopy

Proliferative diabetic retinopathy, defined as the presence of new proliferating blood vessels (neovascularization) arising from the retina or optic disc and growing on the retinal surface or into the vitreous cavity, will be assessed by retinal fundoscopy at Day 270 and Day 365/ET. Retinal fundoscopy must be performed by an ophthalmologist up to 30 days before the Day 270 and Day 365 Visits and, if possible, upon ET. The same ophthalmology practice should be used for all measurements of individual participation. In cases where fundoscopy alone is deemed insufficient, fluorescein angiography may be performed.

Version 1.0 41 Final: 11 Feb 2021

8.4. Safety Assessments

8.4.1. Treatment-emergent Adverse Events and Serious Adverse Events

The definitions of TEAEs and TESAEs can be found in Section 10.2, Appendix 2.

8.4.2. Time Period and Frequency for Collecting TEAE and TESAE Information

All TEAEs and TESAEs will be collected from the Day 180 Visit (Study VMDN-003-2) through Day 365/ET of VMDN-003-2b (see definition of TEAE, Section 10.2).

All TESAEs will be recorded and reported to the Sponsor or designee immediately and under no circumstance should this exceed 24 hours, as indicated in Section 10.2.5. The Investigator will submit any updated TESAE data to the Sponsor within 24 hours of its availability.

Investigators are not obligated to actively seek TEAEs or TESAEs after conclusion of the study participation. However, if the Investigator learns of any TESAE, including a death, at any time after a Participant has been discharged from the study, and he/she considers the event to be possibly, probably, or definitely related to the study intervention or study participation, the Investigator must promptly notify the Sponsor.

8.4.3. Method of Reporting TEAEs, TESAEs and AESIs

The method of recording, evaluating, and assessing causality of TEAEs, TESAEs, and AESIs, and the procedures for completing and transmitting SAE reports are provided in Section 10.2, Appendix 2.

Care will be taken not to introduce bias when identifying TEAEs and/or TESAEs. Open-ended and non-leading verbal questioning of the Participant is the preferred method to inquire about TEAE and TESAE occurrences.

8.4.4. TESAE Reporting to the Sponsor or Designee

All TESAEs should be reported to the Sponsor or designee within 24 hours of knowledge of the TESAE occurring.

8.4.5. Adverse Events of Special Interest

Categories of AESIs

There are three main categories of AESIs: 1) those considered to be related to the angiogenesis potential of Engensis, 2) other medical problems in this patient population, and 3) COVID-19 infections occurring in Participants during the study.

8.4.5.1. **AESIs Related to Angiogenesis**

Atherosclerosis

Hyperplasia of the vasa vasorum in the early stages of atherosclerosis is independent of angiogenesis, but the intimal neovascularization that follows the hyperplasia of the vasa vasorum

Version 1.0 42 Final: 11 Feb 2021

is angiogenesis-dependent.³⁵ Angiogenesis increases oxygen and nutrients to the artery wall and supports initial plaque growth. Once the atherosclerotic plaque develops, intimal angiogenesis is thought to contribute to characteristics of an unstable plaque, plaque hemorrhage, and plaque rupture. Therefore, diagnoses suggestive of recent coronary artery disease or cerebral vascular disease from the Day 180 Visit (VMDN-003-2) to the Day 365/ET Visit (VMDN-003-2b) will be evaluated as AESIs.

Proliferative diabetic retinopathy

Neovascularization is an advanced stage of diabetic retinopathy that is due to relentless abnormal fibrovascular proliferation.³⁶ Because the angiogenic potential of Engensis may promote the development of or stimulate abnormal fibrovascular proliferation in the retina, new fundoscopic changes or symptoms of proliferative diabetic retinopathy that occur from the Day 180 Visit (VMDN-003-2) to Day 365/ET (VMDN-003-2b) are considered AESIs.

Cancer

Angiogenesis plays an important role in the proliferation and metastatic spread of cancer as these processes are dependent on an adequate supply of oxygen and nutrients and removal of waste products.³⁷ All types of cancer reported between the Day 180 Visit (VMDN-003-2) to Day 365/ET (VMDN-003-2b) will be deemed to be AESIs.

Diabetes mellitus and obesity (BMI ≥30) each increases the risk of several types of cancer. ^{38,39} In type 2 DM, there is a 2- to 3-fold increased risk for pancreatic cancer, a 2-fold increased risk for hepatobiliary and endometrial cancers, a 50% increased incidence of colorectal cancer, and a 20% increased risk for breast cancer. ⁴⁰ Obese postmenopausal women have an increased risk of breast cancer, ⁴¹ and obesity is associated with a modestly increased risk of colorectal cancer, ^{42,43} pancreatic cancer, ⁴⁴ and prostate cancer. ⁴⁵

8.4.5.2. AESIs Related to Other Medical Problems

Several medical problems are frequently observed in patients with diabetic peripheral neuropathy that should be considered AESIs. These medical problems are listed below by type of medical problem.

Infections and Infestations; Skin and Subcutaneous Disorders

Because patients with diabetic peripheral neuropathy are at an increased risk to develop skin lesions (e.g., blisters, ulcers) and various lower limb infectious complications (e.g., cellulitis, osteomyelitis) that may be associated with systemic infections (e.g., bacteremia, sepsis, or septic shock), all of these types of medical problems that occur between the Day 180 (VMDN-003-02) and the Day 365/ET (VMDN-003-2b) Visits will be considered AESIs. In addition, any amputations involving the lower extremity, development of Charcot foot, or other similar complications will also be considered AESIs.

Peripheral Arterial Disease

An overlap of DPN and peripheral artery disease (PAD) apparently exists in type 2 diabetic patients. ⁴⁶ Because Participants with DPN may develop signs or symptoms of PAD between the Day 180 (VMDN-003-2) and the Day 365/ET (VMDN-003-2b) Visits, detailed evaluations of Participants considered to have PAD will be considered AESIs.

Version 1.0 43 Final: 11 Feb 2021

Diabetic Neuropathies

Because Participants in this study may develop other types of diabetic peripheral neuropathies while in the study, the following events will be considered to be AESIs in Participants with DPN: diabetic mononeuropathy, diabetic mononeuropathy multiplex, and diabetic polyradiculopathy. The occurrence of these other types of peripheral neuropathies in a Participant with DPN may indicate a more severe form of DPN.

Because Participants in this study may develop various manifestations of autonomic neuropathy (typically involves the gastrointestinal, genitourinary tract, cardiovascular systems) after randomization, the clinical manifestations of diabetic autonomic neuropathy will be considered to be AESIs.

Glycemic Control

Hypoglycemia, hyperglycemia, hyperlipidemia, hypercholesterolemia, and hypertriglyceridemia are to be listed as AESIs based on the Common Terminology Criteria for Adverse Events (CTCAE) grading if they are Grades 3 or 4.

Metabolic complications of DM (such as diabetic ketoacidosis [DKA], hyperglycemic hyperosmolar non-ketotic coma, lactic acidosis, metabolic acidosis [overlaps with DKA]) are to be listed as AESIs.

